1.1.3 Medical Plausibility for Enzyme Replacement Therapy for LAL Deficiency

LAL Deficiency resembles other lysosomal storage disorders (LSDs) with the accumulation of substrate in a number of tissues and cell types. The successful treatment of Gaucher disease with placental glucocerebrosidase in the 1990s and, with the follow-on enzyme produced by recombinant deoxyribonucleic acid (DNA) technology, established the medical value and long-term safety of enzyme replacement therapy (ERT) for LSDs (Barton, 1990, *Proc Natl Acad Sci*; Barton, 1991, *N Engl J Med*). The scientific concepts established by these initial studies have now been extended to a broader range of disorders including Pompe Disease (Kishnani, 2007, *Neurology*; van der Ploeg, 2010, *N Engl J Med*), Fabry disease (Wilcox, 2004, *Am J Hum Genet*), Mucopolysaccharidosis I (Wraith, 2004, *J Pediatr*), and Mucopolysaccharidosis II (Muenzer, 2007, *Mol Genet Metab*), and there is now extensive clinical experience of long-term ERT in patients with lysosomal storage disorders.

In LAL Deficiency, substrate accumulation is most marked in cells of the reticuloendothelial system, including Kupffer cells in the liver, histiocytes in the spleen and macrophages in the lamina propria of the small intestine. Reticuloendothelial cells express the macrophage mannose/N-acetylglucosamine receptor (also known as macrophage mannose receptor [MMR] or CD206), which mediates binding, cell uptake and lysosomal internalization of proteins with N-acetylglucosamine (GlcNAc) or mannose terminated N-glycans, and provides a pathway for the potential correction of the enzyme deficiency in these key cell types (Stahl, 1978, *Proc Natl Acad Sci*). This knowledge and the precedent established for other LSDs provides plausibility that ERT with sebelipase alfa, which has the appropriate glycan characteristics for targeting macrophages and other key cells, will benefit patients with LAL Deficiency.

1.2 Investigational Agent

Sebelipase alfa (SBC-102) is a recombinant human lysosomal acid lipase (rhLAL) with the same amino acid sequence as the native enzyme. Sebelipase alfa is a highly purified recombinant form of the naturally occurring human lysosomal acid lipase enzyme responsible for the metabolism and degradation of cholesteryl esters and triglycerides that are delivered to lysosomes by a variety of routes including low-density lipoprotein (LDL) receptor mediated endocytosis. Sebelipase alfa is a glycoprotein with a molecular weight of approximately 55 kD with 5 N-linked glycosylation sites.

Sebelipase alfa is produced by recombinant DNA technology in egg white using a transgenic *Gallus* expression system and contains predominantly GlcNAc and mannose terminated N-linked glycan structures, some of which contain mannose-6-phosphate (M6P). GlcNAc and mannose terminated glycans are specifically recognized and internalized via the MMR present on the surface of macrophages. These cells are one of the most important cell types that accumulate cholesteryl esters and triglycerides in patients with LAL Deficiency. In addition, the presence of M6P allows delivery to cells that display the widely expressed M6P receptor.

1.3 Nonclinical Data

Sebelipase alfa demonstrated uptake and localization to lysosomes in *in vitro* studies in macrophages. In human fibroblasts deficient in LAL enzyme activity, sebelipase alfa corrected the enzyme deficiency at a cellular level in a dose-dependent manner. In a nonclinical disease model of LAL Deficiency, intravenous (IV) administration of sebelipase alfa restored enzyme activity in key target tissues including the liver. Correction of enzyme deficiency was associated with a marked reduction in the accumulation of cholesteryl esters and triglycerides relative to a placebo treated group in the liver and spleen. In other tissues, including gut and lymph nodes, substrate reduction by sebelipase alfa was demonstrated by a decrease in oil red staining (Quinn, 2010, *American Society of Human Genetics Annual Meeting*).

Homozygous LAL deficient rats demonstrate liver abnormalities, which resemble the abnormalities seen in patients with LAL Deficiency including hepatomegaly, transaminase elevation, and hepatic accumulation of cholesteryl esters and triglycerides. In addition, the LAL-deficient rats show a marked increase in organ (liver, spleen, small intestine) size and substantial histopathological abnormalities due to substrate accumulation compared with wild type controls, as well as markedly impaired weight gain resembling that in patients with LAL Deficiency presenting in infancy. Once weekly (qw) and every other week (qow) administration of sebelipase alfa by IV injection administered over a 4 week period led to a statistically significant improvement (p < 0.05) in weight gain and organ size compared to placebo-treated LAL deficient rats. Improvements in weight gain were statistically significant within 2 weeks of initiation of the first dose. Liver abnormalities were all markedly improved with sebelipase alfa treatment. Additional discussions of the dose response of the effects seen in the nonclinical model are included in Section 1.5.

There were no meaningful toxicological findings in 4-week repeat dose toxicology studies in the Sprague-Dawley rat and Cynomolgus monkey administered intravenous infusions of sebelipase alfa at doses up to 50 mg/kg once weekly. In a 6-month repeated dose toxicity study in Cynomolgus monkeys administered qw IV infusions of sebelipase alfa at doses of 3 mg/kg, 10 mg/kg or 30 mg/kg (5 males and 5 females per dose group), or placebo infusions (5 males, 5 females), sebelipase alfa was well tolerated up to the highest dose level of 30 mg/kg. There were no sebelipase alfa related changes in any of the study parameters, although there was an apparent infusion reaction observed in one animal on Day 1 of dosing following administration of sebelipase alfa at a dose of 10 mg/kg. With Benadryl pretreatment, no additional reactions were observed during the subsequent 25 infusions in this animal. No infusion reactions were observed in a total of 754 infusions administered to the other 29 animals in this study. These results support the long-term dosing with sebelipase alfa.

As expected, based on the number and composition of glycan structures, pharmacokinetic (PK) studies in Sprague-Dawley rats administered IV bolus injections of sebelipase alfa at doses of 1 mg/kg and 5 mg/kg demonstrate that sebelipase alfa is rapidly cleared from the circulation and uptake appears to be saturable. Based on these data, sebelipase alfa is anticipated to have a short plasma half-life in humans.

1.4 Clinical Data

The clinical development program is investigating the safety and tolerability of sebelipase alfa and its clinically meaningful effects on the medical complications of LAL Deficiency. LAL-CL01, a Phase 1/2 dose-finding study in adults with LAL Deficiency, has completed. An extension study, LAL-CL04, is ongoing in subjects who completed LAL-CL01. LAL-CL03 is an ongoing Phase 2/3 study to evaluate the safety, tolerability, efficacy, PK and pharmacodynamics of sebelipase alfa in pediatric subjects with LAL Deficiency who developed growth failure or other clinical evidence of rapidly progressive LAL Deficiency before 6 months of age. LAL-CL02 is an ongoing Phase 3 study to evaluate efficacy, safety, and PK of sebelipase alfa or placebo in pediatric and adult subjects with LAL Deficiency. LAL-CL06 is a Phase 2 study in a broad population of subjects \geq 8 months with LAL Deficiency who may not have been eligible for other studies. LAL-CL08 is a Phase 2 study in infant subjects with rapidly progressive LAL Deficiency. Please refer to the IB for further information on the clinical experience with sebelipase alfa.

Extensive human experience exists for ERTs in the treatment of other lysosomal storage disorders including Gaucher, Pompe, and Fabry disease. While these diseases have distinct clinical manifestations and demonstrate differences in the targeting and biological effects of the ERT, there are relevant data from these studies which inform the use of investigational products of this class. Most of the AEs associated with clinical use of ERTs relate to infusion associated events which occur typically either during or within several hours following completion of the infusion. Given the propensity for infusion reactions with ERT administration, measures have been incorporated in this protocol to minimize risk and monitor subject safety.

1.5 Dose Rationale and Risk/Benefits

1.5.1 Dose Rationale

In this extension study, each individual subject will receive a starting dose of sebelipase alfa equivalent to the dose that he/she received during the fourth infusion of sebelipase alfa in study LAL-CL01. This starting dose is contingent upon that dose being deemed safe and well tolerated following evaluation of safety data for all subjects receiving that dose in study LAL-CL01.

Subjects with LAL Deficiency are expected to require long-term treatment with ERT. Reducing the frequency of infusions during maintenance therapy would lessen the burden of therapy on these patients, thereby improving quality of life and possibly patient compliance. In this study, subjects will transition to a qow dosing regimen after Week 4 (after the first 4 infusions in the extension study). Each subject will be expected to transition to a dose of 1 mg/kg qow or 3 mg/kg qow, which based on the currently available preclinical data is expected to provide a therapeutic benefit:

- In a 4-week study, the minimum effective dose of sebelipase alfa in the nonclinical model of LAL Deficiency was 0.35 mg/kg qw, and was generally comparable to the PD effects of sebelipase alfa at a dose of 1 mg/kg qow. These data suggest that a qow dose < 1 mg/kg has a decreased probability of demonstrating efficacy.
- In a nonclinical model of LAL Deficiency, the PD effects of sebelipase alfa were broadly comparable at the two highest qw dosing regimens (3 mg/kg qw and 5 mg/kg qw) and the two highest qow dosing regimens (3 mg/kg qow and 5 mg/kg qow) studied. These data indicate that 3 mg/kg is a maximally effective dose with both qw and qow administration.
- In patients with late onset LAL Deficiency, substrate accumulation and pathology are most prominent in the liver and spleen. Dose response analysis in the preclinical model demonstrates that substrate is markedly reduced in these organs with a 3 mg/kg qow regimen, and that a 1 mg/kg qow regimen is also effective, but can be differentiated from the 3 mg/kg qow regimen based on effects on growth and liver cholesteryl ester substrate content.

All planned doses of sebelipase alfa in the extension study are anticipated to be safe and well tolerated based upon the following:

- The Investigational Medicinal Product (IMP) has an amino acid sequence identical to the natural enzyme with no engineering of enhancements in biological activity.
- Knowledge of the biochemistry of LAL Deficiency and the mode of action of sebelipase alfa do not raise concerns for unexpected toxicity in humans.

Page **18** of **76**

- There were no meaningful toxicological findings in 4-week repeated dose toxicology studies in the Sprague-Dawley rat and Cynomolgus monkey at doses up to 50 mg/kg. Based on the human equivalent doses in rats (8.1 mg/kg) and monkeys (16.1 mg/kg), this represents a 2.7-to 5.4-fold safety margin relative to the proposed top dose in the current study (3 mg/kg).
- Sebelipase alfa was well-tolerated in a 6-month repeated dose toxicity study in Cynomolgus monkeys treated qw at doses up to 30 mg/kg, the highest dose level evaluated. Based on the human equivalent dose of 9.7 mg/kg, this represents a 3.2-fold safety margin relative to the proposed top dose in the current study. The absence of any sebelipase alfa related changes in study parameters supports the long-term dosing with sebelipase alfa.
- Safety and tolerability data from study LAL-CL01 are available to inform decisions regarding within-subject dose escalation.
- In general for LSDs, the enzymatic activities and mechanisms for lysosomal targeting are conserved across species. Toxicological studies of this class of therapy consistently demonstrate low systemic toxicity (Andrews, 2008, *Enzyme Replacement Therapies*. *In: Cavagnaro JA, ed. Preclinical Safety Evaluation of Biopharmaceuticals: A Science-Based Approach to Facilitating Clinical Trials.*).

As ERTs have a short plasma half-life and biological activity is primarily driven by enzyme concentrations in the target tissue and the rate of substrate accumulation, sebelipase alfa plasma concentrations are being measured only for analysis of sebelipase alfa pharmacokinetics, and will not routinely be used for decisions regarding changes in dose or dosing frequency.

1.5.2 Risk/Benefit Assessment

As discussed in Section 1.1.2, LAL Deficiency is a very rare disease with no approved therapies that leads to significant morbidity and mortality.

Nonclinical studies conducted in a relevant rodent disease model at pharmacological doses and in other nonclinical species at doses substantially in excess of those proposed in this study, revealed no significant risks.

Extensive clinical experience, with approved enzyme replacement therapies from other LSD indications, is relevant for risk evaluation of sebelipase alfa. The most common AEs associated with administration of approved ERTs (including but not restricted to Cerezyme[®], VPRIV[®], Myozyme[®]/Lumizyme[®], Fabrazyme[®]) are infusion reactions. These are usually mild and can be managed by changes in infusion rate and/or the administration of antipyretics and antihistamines. Severe infusion reactions, including anaphylaxis, and SAEs related to ERT administration occur rarely and can require intensive medical intervention. Anti-drug antibodies (ADAs) have been reported with approved ERTs and these may be associated with altered response to treatment and/or increased risk of infusion reactions.

Based on the results from the completed study LAL-CL01, which showed good tolerability of sebelipase alfa infusions at all dosing regimens studied and no SAEs or IARs, as well as rapid improvements in serum transaminases combined with other evidence of biological activity (refer to the IB for further information), there is a reasonable basis to conclude that sebelipase alfa will continue to demonstrate beneficial effects on disease activity as these subjects resume treatment in the current long-term extension study. Irrespective of the immediate clinical value to the individual patient, the information provided from the current long-term extension study will provide benefit to patients with LAL Deficiency by guiding future clinical development.

Based on current understanding of sebelipase alfa, it was anticipated that the increases in serum lipid levels observed in study LAL-CL01 will not be sustained with continuous treatment. This has now been confirmed.

Given the relatively low level of subject risk relative to the progressive and potentially life-threatening nature of untreated LAL Deficiency, it is concluded that the risks to subjects in this study are reasonable in relation to the anticipated benefits and/or knowledge that can be expected from the results.

Page 20 of 76

2 Study Objectives

2.1 Primary Objective

The primary objective of the study is to evaluate the long-term safety and tolerability of sebelipase alfa in patients with liver dysfunction due to LAL Deficiency.

2.2 Secondary Objective

The secondary objectives are:

- To evaluate the long-term efficacy of sebelipase alfa in patients with liver dysfunction due to LAL Deficiency;
- To characterize repeat-dose pharmacokinetics of sebelipase alfa delivered by IV infusion;
- To determine the effect of sebelipase alfa on pharmacodynamic biomarkers.

2.3 Exploratory Objective

The exploratory objectives are:

- To determine the effect of sebelipase alfa on Health-Related Quality of Life (HRQOL) outcome measures;
- To evaluate the acceptability of an every other week dosing regimen of sebelipase alfa;
- To evaluate liver histology.

3 Study Design

3.1 Overview of Study Design

This Phase 2, open-label, extension study will evaluate the long-term safety, tolerability, and efficacy of sebelipase alfa in adult patients with liver dysfunction due to LAL Deficiency who previously received 4 doses of sebelipase alfa in the Phase 1/2 repeat-dose, dose escalation study (Study LAL-CL01). The study will consist of a screening period, treatment period, and follow-up period.

Subjects who successfully receive all 4 doses of sebelipase alfa in study LAL-CL01 and wish to continue treatment with sebelipase alfa in the extension study will undergo screening assessments to determine study eligibility (Note: Assessments performed in study LAL-CL01 within a defined time period may not need to be repeated at the screening visit; see Appendix A: Schedules of Assessments for further details).

Eligible subjects will initiate treatment in the current extension study at least 4 weeks after their last dose of sebelipase alfa in study LAL-CL01. Each subject will initiate treatment in the extension study at the same once-weekly dose of sebelipase alfa that he/she received during the fourth infusion in study LAL-CL01, i.e., 0.35 mg/kg qw, 1 mg/kg qw, or 3 mg/kg qw. Subsequent modifications to the dose and dosing frequency will be undertaken for individual subjects as outlined below based on observed safety and tolerability and clinical response to treatment. All such decisions will be made jointly by the Investigator and Sponsor.

- At Week 6 (and after at least 4 infusions in the extension study), subjects receiving a starting dose of 0.35 mg/kg qw or 1 mg/kg qw will have their dose changed to 1 mg/kg qow. Similarly, subjects who were receiving a starting dose of 3 mg/kg qw for the first 4 infusions will transition to the 3 mg/kg qow regimen.
- After Week 12, subjects receiving a dose of 1 mg/kg qow may be considered for a dose increase to 3 mg/kg qow based on observed safety and tolerability and/or clinical response to treatment. Refer to Section 6.1 for additional details.
- After Week 12, subjects receiving a dose of 3 mg/kg qow may be considered for a dose adjustment to 3 mg/kg qw based on observed safety and tolerability and/or clinical response to treatment. Refer to Section 6.1 for additional details.
- In the event of poor tolerability at any time during the extension study, the dose may be reduced at the discretion of the Investigator. If a subject cannot tolerate the lowest starting dose (0.35 mg/kg qow) despite measures taken to manage any IARs, he/she will be discontinued from treatment.

Safety, tolerability, and efficacy assessments will be conducted at regular intervals throughout the extension study. In addition, blood samples will be obtained at selected timepoints for analysis of sebelipase alfa PK and biomarkers of sebelipase alfa PD activity. Blood samples will also be collected for an exploratory analysis of potential disease-related biomarkers in this patient population, and HRQOL measures will be assessed through subject questionnaires.

A follow-up visit will be conducted for all subjects at 30 (+7) days after the last dose of IMP.

Page 22 of 76

*After Week 12, a dose adjustment from 1 mg/kg qow to 3 mg/kg qow, or from 3 mg/kg qow to 3 mg/kg qw, may be considered based on safety and tolerability and/or clinical response to treatment. A dose reduction is permitted at any time in the event of poor tolerability.

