Main Inclusion and Criteria for	 Subject understands the full nature and purpose of the study, including possible risks and side effects, and is willing and able to comply with all study procedures and provide informed consent. Subject received all 4 scheduled doses of sebelipase alfa in study LAL-CL01 with no life-threatening or unmanageable study drug toxicity. Female subjects have a negative serum pregnancy test at screening, and are not breast-feeding. Female subjects of childbearing potential are willing and able to use a highly effective and approved contraceptive method(s) from the date of informed consent until 30 days after last dose of IMP.
Evaluation	A subject who meets any of the following exclusion criteria will be ineligible for this study:
	 Clinically significant concurrent disease, serious inter-current illness, concomitant medications, or other extenuating circumstances that, in the opinion of the Investigator, would interfere with study participation or the interpretation of the effects of sebelipase alfa. Clinically significant abnormal values on screening laboratory tests, other than liver function or lipid panel tests. Subjects with an abnormal laboratory value that is of borderline significance may be allowed to undergo repeat testing once within a 30-day period.
	Sebelipase alfa (SBC-102), a recombinant human lysosomal acid lipase (rhLAL) produced in the transgenic Gallus , will be administered by IV infusion. The following dosing regimens of sebelipase alfa may be administered in this study: 0.35 mg/kg qw, 1 mg/kg qw, 3 mg/kg qw, 1 mg/kg qow, and 3 mg/kg qow.
Investigational Medicinal Product, Dose, Route, Regimen	Subjects will initiate treatment in the extension study at least 30 days after their last dose of sebelipase alfa in study LAL-CL01. Each subject will initiate treatment in the extension study at the same once-weekly dose of sebelipase alfa that he/she received during the fourth infusion in study LAL-CL01, i.e., 0.35 mg/kg qw, 1 mg/kg qw, or 3 mg/kg qw. Subsequent modifications to the dose and dosing frequency will be undertaken for individual subjects as outlined below based on observed safety and tolerability and clinical response to treatment. All such decisions will be made jointly by the Investigator and Sponsor:

Page **5** of **76**

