	 At Week 6 (and after at least 4 infusions in the extension study), subjects receiving a starting dose of 0.35 mg/kg qw or 1 mg/kg qw will have their dose changed to 1 mg/kg qow. Similarly, subjects who were receiving a starting dose of 3 mg/kg qw for the first 4 infusions will transition to the 3 mg/kg qow regimen. After Week 12, subjects receiving a dose of 1 mg/kg qow may have their dose increased to 3 mg/kg qow based on observed safety and tolerability and/or clinical response to treatment.
	 After Week 12, subjects receiving a dose of 3 mg/kg qow may be considered for a dose adjustment to 3 mg/kg qw based on observed safety and tolerability and/or clinical response to treatment.
	 In the event of poor tolerability at any time during the extension study, the dose may be reduced at the discretion of the Investigator. If a subject cannot tolerate the lowest starting dose (0.35 mg/kg qw) despite measures taken to manage any IARs, he/she will be discontinued from treatment.
Duration of IMP administration	The duration of each subject's treatment in the study will vary but is expected to be at least 26 weeks and approximately 5 years.
Reference therapy	No reference therapy will be administered in this study.
	Safety The primary safety endpoints will include the incidence of adverse events (AEs) SAEs, and IARs; changes in vital signs (blood pressure, heart rate, respiratory rate, and temperature), physical examination findings, 12-lead electrocardiogram (ECG) parameters, and clinical laboratory tests (CBC/hematology, serum chemistry and urinalysis); use of concomitant medications/therapies; and characterization of anti-sebelipase alfa anti-drug antibodies (ADAs), including ADA positive rate, time to ADA positivity, peak ADA titer, and time to peak ADA titer. The effect of ADAs on the safety of sebelipase alfa will also be explored. A further characterization of ADAs, including inhibitory ADAs, may be performed as a separate pooled analysis across studies, and will be reported separately from this protocol.

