6.1.2 Dose Reduction

Subjects who do not tolerate their current dose level may receive a dose reduction to the next lowest dose level, i.e., 1 mg/kg qow or 0.35 mg/kg qow, at the discretion of the Investigator in consultation with the Sponsor and, where appropriate, the SC.

If a subject cannot tolerate a dose of 0.35 mg/kg qow, despite measures taken to manage any IARs, the subject will be discontinued from the study.

NOTE: Any subject who undergoes a dose modification, as described above, will have additional laboratory monitoring schedule of selected analytes, as detailed in Section 5.1.10.

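### The dose at which intolerance leads to discontinuation is weekly in the synopsis but every other week in Protocol 3.1 and 6.1.2, and Section 7.1.3 and Appendix F conflict on slowing or stopping an infusion

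*Protocol*

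**What the plan says.** **Discontinuation floor.** The synopsis, in its dose and regimen entry, sets the floor with "If a subject cannot tolerate the lowest starting dose (0.35 mg/kg qw"; SAP 3.1 carries the same words. Protocol 3.1 has "If a subject cannot tolerate the lowest starting dose (0.35 mg/kg qow", and Protocol 6.1.2 has "If a subject cannot tolerate a dose of 0.35 mg/kg qow". Section 6.1.2 also names the every-other-week dose as a reduction step: "next lowest dose level, i.e., 1 mg/kg qow or 0.35 mg/kg qow".

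The synopsis lists the regimens that may be given as "0.35 mg/kg qw, 1 mg/kg qw, 3 mg/kg qw, 1 mg/kg qow, and 3 mg/kg qow". Protocol 3.1 gives the starting doses as "0.35 mg/kg qw, 1 mg/kg qw, or 3 mg/kg qw", all weekly.

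The stated consequence differs as well. In Protocol 3.1 it is "he/she will be discontinued from treatment", and the synopsis and SAP 3.1 agree. In Protocol 6.1.2 it is "the subject will be discontinued from the study".

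**Infusion reactions.** Protocol 7.1.3 lists signs of a possible acute infusion-associated reaction (IAR). If one occurs in a subject who has no respiratory symptoms and is hemodynamically stable, the rate must be halved and the infusion carried on. No grade is mentioned. Discontinuing the infusion appears in that section only under severe reactions. Appendix F sorts signs by grade: Grade 1 starts with slowing by 50%, and Grade 2 starts with stopping the infusion.

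**The concern.** The primary objective is long-term safety and tolerability, so the rules for intolerance and for infusion reactions are core procedures here. A subject who cannot tolerate 0.35 mg/kg weekly is discontinued under the synopsis, but may be reduced further under Protocol 3.1 and 6.1.2. A stable subject with urticaria or vomiting keeps receiving a slowed infusion under Section 7.1.3, but has it stopped under the Grade 2 row of Appendix F. About 9 primary centers plus local centers may be giving infusions, and the text does not give them one answer in either situation.

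**Working it through.** No sample size, power or error rate is involved, so the check is a comparison of texts with simple arithmetic.

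**1. The floor, side by side**

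| Place | Floor | Discontinued from |
|---|---|---|
| Synopsis | 0.35 mg/kg qw | treatment |
| Protocol 3.1 | 0.35 mg/kg qow | treatment |
| Protocol 6.1.2 | 0.35 mg/kg qow | study |
| SAP 3.1 | 0.35 mg/kg qw | treatment |

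A one-letter slip in Section 3.1 does not explain this, because Section 6.1.2 uses the every-other-week dose twice, as a reduction step and as the floor. Nor is the body of the protocol consistent within itself: Section 3.1 calls 0.35 mg/kg qow a starting dose, yet every starting dose given in that section is weekly.

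Dose over 14 days = dose per infusion × number of infusions:

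- qw: 0.35 × 2 = 0.70 mg/kg
- qow: 0.35 × 1 = 0.35 mg/kg
- ratio: 0.70 / 0.35 = 2

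The amount per infusion is the same; the amount per unit time differs by a factor of 2. The synopsis lists 5 regimens, and 0.35 mg/kg qow would be a sixth (5 + 1 = 6).

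The protocol's own rationale also separates the two. Section 1.5.1 identifies 0.35 mg/kg qw as the minimum effective dose in the nonclinical model and regards every-other-week doses under 1 mg/kg as less likely to show efficacy.

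**2. Infusion reactions, side by side (stable subject, no respiratory symptoms)**

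| Sign | Protocol 7.1.3 | Appendix F |
|---|---|---|
| Hyperemia/flushing | halve rate, continue | Grade 1: slow; Grade 2: stop |
| Pruritus/itching | halve rate, continue | Grade 2: stop |
| Urticaria | halve rate, continue | Grade 2: stop |
| Vomiting | halve rate, continue | Grade 2: stop |
| Diarrhea | halve rate, continue | Grade 2: stop |
| Abdominal cramping | halve rate, continue | Grade 2: stop |

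Six signs appear both in the 7.1.3 list and under Grade 2. One of them (flushing) is also under Grade 1, which leaves 6 − 1 = 5 under Grade 2 only. The example in 7.1.3, 125 to 62.5 mL/hr, is 62.5 / 125 = 50%. It matches the Grade 1 action and not the Grade 2 action.

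The two lists are not identical. Severe headache is only in Appendix F, and nausea and fever are Grade 1 there; none of these is counted above.

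**The case against.** **On the floor.** Section 6.1.2 makes reductions in consultation with the sponsor and, where appropriate, the Safety Committee, so one party could impose consistency. Every subject entered after four LAL-CL01 doses without unmanageable toxicity, and Section 1.5.2 reports no SAEs or infusion reactions in that study, so intolerance of the lowest dose is a remote event. The SAP states that its design text does not modify the protocol, so SAP 3.1 is a copy and not an independent conflict. The synopsis list says what may be given and does not expressly exclude other regimens. Section 1.5.1 concerns efficacy of the planned transition, not tolerability.

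Much of this stands as a limit on reach. It also means that neither the SAP nor Section 1.5.1 can settle the question. It does not remove the conflict between synopsis and body. The synopsis and Section 3.1 leave the reduction to the investigator's discretion without mentioning that consultation in the same sentence, although Section 3.1 elsewhere makes dose decisions joint.

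**On infusion reactions.** Appendix F describes itself as general guidance and leaves room for clinical judgment. A graded table can be read as refining an ungraded rule. Its Grade 1 row already runs from slowing to stopping if symptoms continue. The Grade 2 row mentions an inhaled beta-adrenergic treatment, so it may reach subjects with respiratory signs, whom the slow-and-continue rule excludes. Item (d) of the severe branch in 7.1.3 mentions moderate reactions.

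The overlap may indeed be incomplete, but the Grade 2 sign list names no respiratory sign or blood pressure change, so a stable subject with urticaria meets both instructions. Item (d) extends only blood sampling and possible skin testing to moderate reactions, not discontinuation. The guidance label does not settle precedence, because 7.1.3 uses mandatory wording and itself sends sites to Appendix F for further detail.

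**Conclusion.** Both contradictions are in the current text and the concern holds. The floor differs by a factor of 2 in dose per 14 days, and one version uses a regimen that the synopsis does not list. For six signs, Section 7.1.3 and Appendix F Grade 2 give opposite instructions in a stable subject, taking both texts literally.

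The limits are real. At most 9 subjects are enrolled, and 0.35 mg/kg qw is scheduled only before Week 6, although a reduction may come at any time over about 5 years. No effect on the listed primary safety endpoints is shown. The exposure summary in SAP 11.1 changes its count of incomplete infusions only if a stopped infusion is not resumed, and the Grade 2 row does not say whether it may be. The treatment-versus-study wording is not claimed to alter follow-up, since Protocol 4.6.2 and Appendix A provide discontinuation assessments and an End of Study visit for subjects who stop early. The point still needs correcting, because it concerns when a subject must be discontinued and what staff do during a reaction.

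**What to change.** The sponsor must reconcile the following, and this review does not say which version is right:

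- **Floor:** the synopsis (regimen list and intolerance rule), Protocol 3.1, Protocol 6.1.2 and SAP 3.1, so that there is one discontinuation floor, one stated consequence (treatment or study) and one list of permitted regimens. Check the result against Section 1.5.1, or state that the rationale there does not bear on reductions for tolerability.
- **Infusion reactions:** Protocol 7.1.3 and Appendix F, so that each situation has one action, or an explicit statement of which text takes precedence.

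The cost is a protocol clarification or amendment with matching text in SAP 3.1. No new data or procedures are needed.
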